Title: Mindfulness-Based-Cognitive-Intervention for African Caribbean Men with Erectile Dysfunction

Study Protocol: ethically approved 20/01/2021

Study commencement: 01/10/2022

Study completion: 01/03/2023

Study protocol including statistical analysis plan

Methods

Design

A mixed study approach was used including a randomised controlled study with an experimental and waitlist control group. Further, a summative content analysis was conducted based on participant feedback responses. Participants were randomly allocated to one of two groups, group 1 (the experimental group receiving MBCI) and group 2 (the control waitlist group). The two groups were compared for differences in MBCI effectiveness in relation to sexual functioning, mindfulness, well-being and sexual self- efficacy (Kendall., 2013). A snowballing sampling method using social media including for example WhatsApp, TikTok, LinkedIn, Facebook was used to research sensitive issues among populations that might be difficult to reach (Browne, 2005). Participants A google form was developed where a link to the study contents was made accessible via Facebook, LinkedIn, Reddit and Twitter. All participants included 68 African Caribbean men with ED aged 18 years and above. Of the sample, 34 had been randomly allocated to group 1 and 34 to group 2. Participants had access to a password-protected laptop/computer and understand English at a suitable level. Further, participants were registered with a GP service (GP will be informed as this is an intervention). Sexuality and the individuals partnered status did not form part of the exclusion criteria. Those without ED, taking prescription medication including Viagra and were not registered with a GP were excluded from this study.

Assessment tools

Demographic Information Demographic information included ethnicity, partnered status, sexuality, age, employment status, children, cancer type, cancer treatment used, other health concerns, sexual difficulties, prescription medications and substance use including alcohol consumption and smoking, and levels of exercise.

The International Index of Erectile Function (IIEF-5) Questionnaire (Rhoden et al., 2002)

Consists of five questions with five response categories measuring erectile functioning. For the purpose of this study, erectile functioning and satisfaction were measured. Response categories

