In accordance with the BPS code of ethics and conduct (internet mediated, 2017) and following ethical approval from LMU ethics review panel, this clinical trial was registered with www.clinical.gov. Those interested in taking part signed a consent form which authorised the principal researcher to contact their General Practitioner (GP). Those accepted onto the programme provided written consent. Baseline questionnaire measures were taken at week 0 and repeated at weeks four and eight. The main exercises included mindfulness, breathing exercises, relaxation techniques, being mindful of the senses and the body and understanding enjoyable sex (adapted Bossio et al., 2018). Four one-to-two-hour online weekly group sessions took place over the duration of one month. Feedback on the intervention was sought throughout the intervention using Mentimeter, by which a content analysis of participants' experiences was conducted at each point. Participants were ensured confidentiality with respect to their engagement in the programme and anonymity. They were also reminded that they could withdraw from the study at any point and with no repercussions and did not have to answer all the assessment questions. Researchers in the team had experience of working in healthcare with vulnerable and diverse groups. They had been versed with the distress protocol prior to the research being started to support the recognition of distress among the participants. All responses generated from participants in this study were stored on a password protected

computer in accordance with the General Data Protection Regulation (2018); Data Protection Act (2018).

Statistical analyses

A mixed ANOVA was used to compare means of study variables measured across weeks 0, 4, and 8 weeks for both groups (experimental and control). A series of paired samples t-tests compared dependent variables pre- and post- tests and follow-up outcomes. Nonparametric Mann-Whitney was used to compare acquired and lifelong ED with substance use, medication use, alcohol consumption, exercise, and smoking. Feedback was taken from participants at weeks 0, 4 and 8 of the MBCI intervention and a summative content analysis using non parametric data analysis was used to analyse secondary data outcomes.

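### The comparison of acquired with lifelong ED on five lifestyle items takes no account of age, so a crude difference could reflect age if the two ED types differ in age

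*Combined protocol and SAP*

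**What the plan says.** The sentence at issue is in Statistical analyses: "Nonparametric Mann-Whitney was used to compare acquired and lifelong ED with substance use, medication use, alcohol consumption, exercise, and smoking". No covariate, stratification, matching or regression is attached to it.

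The participant description in Methods gives the sample: "All participants included 68 African Caribbean men with ED aged 18 years and above", with no upper age limit. Allocation is to treatment: "Of the sample, 34 had been randomly allocated to group 1 and 34 to group 2". Nothing is randomised by ED type.

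Under Assessment tools, age is on the demographic form ("Demographic information included ethnicity, partnered status, sexuality, age, employment status"), and the lifestyle items are on the same form ("prescription medications and substance use including alcohol consumption and smoking, and levels of exercise"). The main model does not use age either: "A mixed ANOVA was used to compare means of study variables measured across weeks 0, 4, and 8 weeks for both groups".

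The documents do not define acquired or lifelong ED. They give no counts or age distribution by ED type, no association between age and any habit, and no significance level for these tests.

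**The concern.** This is an observational comparison inside a randomised trial. Randomisation to MBCI or waitlist does nothing to balance age between the ED types. On the ordinary meaning of the words, acquired ED begins after a period of normal function and lifelong ED does not. In a sample open to adults of any age, it is therefore reasonable to expect that men with acquired ED may be older. Drinking, smoking, exercise and medication use can all plausibly vary with age. If both hold, the unadjusted test picks up the age difference and shows it as a lifestyle difference.

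Timing is a second limit. In lifelong ED, the habits recorded at entry come after the ED began, so a difference cannot be read as its cause. Age adjustment does not repair this; only the wording of the conclusion can.

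What is at stake is how an ancillary result is interpreted. Apart from describing the sample, these tests are the only analysis the document names for the lifestyle items.

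**Working it through.** The plan gives no figure to reproduce for this comparison, so the check shows how the mechanism behaves under stated assumptions.

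**From the documents:** 68 men in total; Mann-Whitney; five items; age recorded.

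**Assumed:** the split by ED type, the age gap, the strength of the age-habit relation, a five-level habit score and a two-sided 5% level. In every scenario the habit depends on age only, with no ED-type effect at a given age. Each cell has 3,000 simulated samples, so the simulation error around 5% is √(0.05 × 0.95 / 3000) = 0.4 percentage points.

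**1. Scenarios in years.** 20 lifelong and 48 acquired, age SD 12, log-odds slope 0.02 to 0.06 per year. Ranges cover the slopes and repeat runs.

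| Age gap | Gap in SD | Mann-Whitney rejects |
|---|---|---|
| 5 years | 5/12 = 0.42 | 5-9% |
| 10 years | 10/12 = 0.83 | 7-20% |
| 15 years | 15/12 = 1.25 | 8-39% |

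A linear model of the ranks on ED type and age rejects in 4-6%.

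**2. Scenarios in SD units.** Habit = ρ × age + √(1 − ρ²) × noise, cut into five levels. The crude shift between ED types on the underlying scale is ρ × gap; for example, 0.3 × 1.0 = 0.30 SD. Mann-Whitney rejection rates:

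| Age gap (SD) | Split | ρ = 0.2 | ρ = 0.3 | ρ = 0.5 |
|---|---|---|---|---|
| 0.5 | 34/34 | 6.0% | 9.3% | 15.4% |
| 0.5 | 48/20 | 6.5% | 7.5% | 14.0% |
| 1.0 | 34/34 | 11.0% | 18.8% | 47.0% |
| 1.0 | 48/20 | 10.8% | 19.1% | 41.5% |
| 1.5 | 34/34 | 21.1% | 39.1% | 81.2% |
| 1.5 | 48/20 | 18.6% | 34.8% | 73.4% |

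With no age gap, or with ρ = 0, the rate is 4.1% to 4.8%. The age-adjusted rank model gives 4.3% to 6.8% throughout. Both conditions are needed for the effect, and adjustment removes it.

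**3. Cost in precision.** Adding age multiplies the standard error for ED type by at most about √(1 + p(1 − p)d²), where p is the share of one ED type and d the age gap in SD. With p = 20/68, p(1 − p) = 0.208:
- 5 years: √(1 + 0.208 × 0.174) = 1.02
- 10 years: √(1 + 0.208 × 0.694) = 1.07
- 15 years: √(1 + 0.208 × 1.5625) = 1.15

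Simulation gives an increase of 8-15% at 15 years. It is below the ceiling where age also explains part of the habit.

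**4. Sparse yes/no items.** Ordinary logistic regression has no finite ED-type estimate when one type answers all no (or all yes). With equal prevalence in both types, the chance that at least one type is all no is:
- at 10%: 0.9^20 + 0.9^48 − 0.9^68 = 0.122 + 0.006 − 0.001 = 0.127
- at 5%: 0.95^20 + 0.95^48 − 0.95^68 = 0.358 + 0.085 − 0.031 = 0.413

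Simulated with a 10-year gap and slope 0.04, the figures are about 16-18% and 45%. Low prevalence is plausible for medication because of the entry rule: "Those without ED, taking prescription medication including Viagra and were not registered with a GP were excluded from this study".

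**The case against.** The strongest reply is that the plan never asks an age-independent question. It says only that the two ED types are compared. For that crude question Mann-Whitney tests its own null hypothesis correctly: if older men with acquired ED drink differently, the groups do differ and rejection is right. The rejection rates above are false positives only for a comparison at equal age. The documents state no causal or risk-factor hypothesis. This stands, and it is why the crude test should be kept.

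The second reply is that both conditions for the effect lie outside the documents. This also stands. The two sets of assumptions give upper ends of 39% and 81%, so the figures show a possible mechanism and do not size a problem in this trial.

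Third, age is not the only candidate; partnered status and other health concerns are recorded too. That is fair, but 68 men with an unknown split support few covariates, and age has the plainest reason to differ between the types.

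A reader might infer that the planned tests are invalid, that age is known to confound them, or that all five must be replaced. The documents support none of these readings.

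What survives is narrower. With no report of age by ED type and no adjusted result, nobody can tell an association between a habit and ED type from a difference in age.

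**Conclusion.** The point holds as a minor improvement. The five comparisons are crude contrasts between non-randomised groups, age is available and unused, and a significant result could reflect age if age differs between the ED types and relates to the habit. Whether it would do so here is unknown.

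Under the assumptions shown, the chance of a significant crude result with no ED-type effect at a given age runs from near the nominal 5%, for a small gap and weak relation, to 39% at a 15-year gap in the scenarios in years. It reaches 81% in the most extreme of the scenarios in SD units. It stays near 5% if either condition is absent. The comparison is ancillary, and the trial's conclusion about MBCI against waitlist does not depend on it.

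**What to change.** Using data already collected:

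- Define acquired and lifelong ED, and report the number of men and the age distribution for each.
- Keep each Mann-Whitney result, labelled as the crude, unadjusted comparison.
- Beside it, give an age-adjusted comparison with a confidence interval: rank or ordinal regression with age as a continuous covariate for graded items, and penalised (Firth) logistic regression for yes/no items, because sparse cells are likely.
- Base any statement of a link between a habit and ED type on the age-adjusted result.
- Label all five as exploratory associations, not risk factors. No multiplicity handling is stated either; five independent tests at 5% would give 1 − 0.95^5 = 22.6% chance of at least one false positive.
- Reconcile the medication comparison with the entry rule that excludes men on prescription medication, so that it is clear what the item can measure.

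The cost is a little more analysis. The standard error for ED type hardly changes at a 5-year age gap and is up to roughly 15% larger at a 15-year gap (age SD 12, 20/48 split, all assumed). A very uneven split or a rare item would leave wide intervals, which should be reported as such.
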